Neuromuscular electrical stimulation for the treatment of jaw-closing dystonia

NCT03889704

STUDY18120054

[name], DPhil, FRCP

University of Pittsburgh

15 June 2021

Study Title	Neuromuscular electrical stimulation for the treatment of jaw-closing dystonia
Study Design	6 patients with jaw-closing dystonia will be treated with neuromuscular electrical stimulation over 8 weeks. The distance the mouth can be opened voluntarily, and the oromandibular dystonia questionnaire (OMDQ-25) will be employed to determine whether there is any objective change in jaw opening or evidence of functional improvement.
Primary Objective	(1) Measure whether neuromuscular electrical stimulation increases inter-incisor (or inter-gum) distance in patients with jaw-closing dystonia as an objective measurement of jaw opening. (2) Assess whether neuromuscular electrical stimulation alters quality-of-life in patients with jaw-closing dystonia.
Secondary Objective(s)	(1) Determine effect size, variability and distribution of data to allow rational design of a larger study if the intervention looks promising.
Research Intervention(s)/ Investigational Agent(s)	Omnistim® FX ²
IND/IDE #	
Study Population	Adult male and female patients with jaw-closing dystonia
Sample Size	6
Study Duration for individual participants	8 weeks
Study Specific Abbreviations/ Definitions	NMES: neuromuscular electrical stimulation PNES: patterned electrical neuromuscular stimulation PD: Parkinson's disease PSP: progressive supranuclear palsy AD: Alzheimer's disease TDQ: tongue depressor quantity OMDQ-25: oromandibular dystonia questionnaire

Objectives

1. Measure whether neuromuscular electrical stimulation increases inter-incisor (or inter-gum) distance in patients with jaw-closing dystonia as an objective measurement of jaw opening.
2. Assess whether neuromuscular electrical stimulation alters quality-of-life in patients with jaw-closing dystonia.
3. Determine effect size, variability and distribution of data to allow rational design of a larger study.

Background

This pilot study is designed to acquire initial data on whether neuromuscular electrical stimulation might be useful for the treatment of jaw-closing dystonia.

Study design

Open-label pilot study.

Study Primary Endpoints

1. Measure whether neuromuscular electrical stimulation increases inter-incisor (or inter-gum) distance in patients with jaw-closing dystonia as an objective measurement of jaw opening, both before and after each treatment session, and from baseline to the end of the study.
2. Assess whether neuromuscular electrical stimulation alters quality-of-life in patients with jaw-closing dystonia by measuring change in OMDQ-25 from baseline to the end of the study

Study Intervention/Investigational Agent

Omnistim® FX² neuromuscular stimulation device, set to "*muscle spasm reduction*". The United States Food and Drug Administration has determined that the Omnistim® FX² device is substantially equivalent to other legally marketed predicate devices to be marketed within the provisions of the Federal Food, Drug, and Cosmetic Act.

Procedures Involved

6 patients will be enrolled in the study and written informed consent will be obtained at the beginning of the study prior to the first session.

Each participant will participate in 16 sessions over the 8 weeks of the study.

The electrodes will be placed over bilateral masseters using a bipolar technique; on each side, one electrode will be placed over the motor point, and one electrode will be placed over the belly of the muscle. The Omnistim® FX² device will be set to the "*muscle spasm reduction*" and electrical stimulation will last 20 minutes, during which time the patient will be directly supervised by the treating physician. After completion of stimulation, electrodes will be removed, and the patient's skin will be cleaned and examined for hyperemia and irritation. At

the end of each individual patient session, the equipment will be cleaned with germicidal wipes, including the control panel and lead wires. The electrodes are disposable and will be discarded after single use.

The severity of jaw-closing dystonia will be measured using 2 methods:

1. Determine how many stacked tongue depressors the patient is able to fit safely between their front incisors (tongue depressor quantity, TDQ). In the case of edentulous patients who are not able to wear their dentures because of dystonia, we will measure the distance between the front gums using the same method. TDQ is a simple rapid measurement that is carried out routinely in speech therapy practice for evaluation and conservative treatment of jaw opening problems. This will be measured before and after each treatment session.
2. The impact of jaw-closing dystonia on the patient's functional status will be determined using the oromandibular dystonia questionnaire (OMDQ-25), which has been shown to be both a valid tool to assess quality-of-life in oromandibular dystonia and sensitive to change after botulinum toxin treatment (Merz et al. 2010). OMDQ-25 will be evaluated at baseline and after each treatment session.

Data and Specimen Banking

All data will be de-identified, with each participant being assigned a study number, and all study documents aside from consent forms will be labeled only with this identifier. De-identified data will be digitized for analysis and stored on a UPMC server in a password-protected user account. There will be no specimen banking.

Sharing of Results with Subjects

Results will be shared with the subjects upon completion of the study.

Study Timelines

Each patient will undergo 16 sessions total, for a total of 8 consecutive weeks (or fewer sessions if individual patients experience discomfort or other problems).

Inclusion criteria:

1. Jaw-closing dystonia, which may be primary or secondary to a neurodegenerative disease or medications.
2. Unable to voluntarily open jaw fully on examination.
3. Evidence of functional impairment resulting from dystonia including inability to completely open the jaw during speaking or eating to such an extent that it interferes with these tasks.
4. Patient interested in participating, and willing to attend multiple treatment sessions in the neurology clinic.

Exclusion criteria:

1. Presence of a cardiac pacemaker, implanted defibrillator, or other implanted electronic device
2. Inability to provide consent (either by the patient, spouse or an identified power of attorney)
3. Age 18 years or younger
4. Pregnancy

Vulnerable Populations

Our study population potentially includes adults with neurodegenerative diseases who may also have cognitive impairment. In the case of severe cognitive impairment that precludes the patient giving *bona fide* informed consent, this will be given instead by the patient's power of attorney (POA), spouse, or adult son or daughter. In this case, treatment will only be carried out with the patient's clear and unequivocal assent. If no POA, spouse, or child is identified, then the patient will be excluded from the study.

Local Number of Subjects

6 patients will be recruited in total for this pilot study.

Withdrawal of Subjects

Patients will be withdrawn from the study if they experience hyperemia at the electrode placement sites that does not resolve between patient sessions, or if they experience more than mild discomfort that requires complete termination of neurostimulation at any point during the course of the study. Patients will also be withdrawn from the study if they experience muscle fatigue or weakness which interferes with daily functions like speaking or chewing food. Placement of a cardiac pacemaker, implanted defibrillator, or other implanted electronic device at any point during the study will also lead to withdrawal.

Risks to Subjects

Prior work using NMES to treat oropharyngeal dysphagia suggests that adverse events can include a burning sensation during treatment, skin irritation and soreness at the electrode site, neck pain, jaw pain, and headache.

Potential Benefits to Subjects

Patients may experience functional improvement in activities impaired by jaw-closing dystonia, including speaking, chewing, mouth opening for oral hygiene, comfort, eating, drinking.

Data Management and Confidentiality

All data collected will be stored in a locked office room and de-identified, with each participant being assigned a study number, and all study documents aside from consent forms will be labeled only with this identifier. A single hard copy key document will relate each participant's identity to their study number. De-identified data will be digitized for analysis and stored on a server in a password-protected user account.

Provisions to Monitor the Data to Ensure the Safety of Subjects

A data and safety monitoring plan will include quarterly meetings to discuss issues regarding enrollment, status of the visits, recruitment, data coding and entry and/or address any adverse events, issues or concerns at that time.

Provisions to Protect the Privacy Interests of Subjects

Research data will be de-identified using a subject number. The only patient identifiable data will be the consent form and the 'key' list relating the participant number to their name, both of which will be stored in a locked filing cabinets in a locked office. Data digitized for analysis will be de-identified and stored in password-protected files on servers in password-protected accounts.

Economic Burden to Subjects

Patients will be given a voucher for free parking to attend study visits.

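### Does primary endpoint 1 need to say whether the end-of-study tongue depressor reading is the one before or after the last session?

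*Protocol*

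**What the plan says.** In the Protocol, Study Primary Endpoints, item 1 sets two contrasts on one measure, inter-incisor or inter-gum distance: "both before and after each treatment session, and from baseline to the end of the study". Under Procedures Involved, the distance is measured as the number of stacked tongue depressors that fit between the front teeth or gums (TDQ), and "This will be measured before and after each treatment session". The same section says "Each participant will participate in 16 sessions over the 8 weeks of the study". No separate end-of-study visit or non-treatment reading is described.

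Study Timelines allows 16 sessions "or fewer sessions if individual patients experience discomfort or other problems", so a patient's last session may come before the sixteenth. For the second primary endpoint, the quality-of-life questionnaire, "OMDQ-25 will be evaluated at baseline and after each treatment session", so every questionnaire score after baseline is post-session.

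Objectives, item 3 gives the pilot's further purpose: "Determine effect size, variability and distribution of data to allow rational design of a larger study". Under Local Number of Subjects, "6 patients will be recruited in total for this pilot study".

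**The concern.** The endpoint separates an immediate effect (within a session) from a sustained one (over 8 weeks), but does not say which reading at the last session closes the 8-week interval. If it is the post-session reading, the sustained contrast also contains the immediate effect of the stimulation just given. A treatment that loosens the jaw for an hour and leaves nothing behind could then be reported as producing an 8-week gain. For a patient who attended only one session, the two contrasts would be the same number.

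Two features might tilt an analyst towards the post-session value: it is the last reading recorded, and it matches the timing of the questionnaire. The trial is open-label, so the choice could be made after the data are seen. The result is also meant to inform the design of a larger study, so an effect that mixes the immediate and the sustained could be carried forward under the wrong label.

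**Working it through.** The protocol states no effect size, standard deviation, significance level or power, so there is no planned figure to reproduce. The check is a reading of the schedule plus simple algebra.

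**Readings available (Procedures Involved).** With 16 sessions there are 2 × 16 = 32 TDQ readings per patient and 1 + 16 = 17 questionnaire scores. No separate TDQ baseline is scheduled, so I take the reading before session 1 as baseline (an assumption, but the natural one).

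**The two candidate contrasts.** Let the last attended session be k, and define

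- L = pre_k − pre_1, the change that persists to the start of the last session
- d = post_k − pre_k, the acute change in that session

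Then

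- pre-session end value: pre_k − pre_1 = L
- post-session end value: post_k − pre_1 = (pre_k − pre_1) + (post_k − pre_k) = L + d

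The two agree only if d = 0. With assumed values in depressors:

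| L | d | Pre-session end value | Post-session end value |
|---|---|---|---|
| 0 | 1 | 0 | 1 |
| 1 | 1 | 1 | 2 |
| 2 | 0 | 2 | 2 |

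**Can the two be told apart afterwards?** Yes. Both readings of session k are scheduled, so d is observed for each patient with both, and (L + d) − d = L. If the within-session result is reported only as an average over sessions, a reader of the summary recovers L approximately; the analyst, holding the data, recovers it exactly.

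**What the pre-session choice would cost.** The reading before session k reflects only k − 1 sessions. If benefit accrued equally per session (an assumption), it would understate the total by 1/k: 1/16 = 6.25% with 16 sessions, 1/8 = 12.5% with 8, 1/2 = 50% with 2. It also captures only benefit that lasts from one visit to the next. Spread evenly, which the protocol does not state, 16 sessions over 56 days means 56/16 = 3.5 days between visits. Finally, it would put the TDQ end value before the last session and the questionnaire end value after it. For a patient with k = 1 it is pre_1 − pre_1, which carries no information.

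**Consequences for testing and planning.** Assume a two-sided 5% paired t test with n = 6 and L = 0; the protocol specifies no test. The pre-session contrast is then nominally significant 5% of the time. The post-session contrast is significant 8%, 17%, 51% and 83% of the time for d = 0.25, 0.5, 1.0 and 1.5 standard deviations of the change. These are error rates only if the question is about L. If the question is about L + d, the same figures are power.

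The same holds for sample size. A larger study sized on L + d but aimed at L, with the same standard deviation, would have 1/(1 + d/L)² of the patients it needs: 64%, 44% and 25% for assumed d/L of 0.25, 0.5 and 1. If it aimed at L + d, there would be no shortfall. The protocol does not say which it would target.

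**The case for a change.** The best case for a change is that this is not a choice of model or test: it concerns which measurement, at which time, is the primary endpoint. The protocol distinguishes immediate from sustained change and then words the sustained part so that it can include the immediate part. A sentence of wording would settle it, with no extra visits, and would remove a choice that could otherwise be made with the data in view.

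Part of this stands. No section resolves the point, the identity is exact, and deciding before the data are examined is better practice than deciding after. What does not stand is the step from there to a defect in the protocol. It names the variable, the instrument, the reading times and the contrast, and states nothing false or contradictory. That the post-session value would be used is inference: no section says the two primary endpoints are to share timing, and the last value recorded need not be the one analysed. The harm to a larger study depends on assumed d/L and on a target the protocol does not set.

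A further argument, that patients withdrawn for "more than mild discomfort that requires complete termination of neurostimulation at any point during the course of the study" would have post-session readings after an incomplete stimulation, over-reads Withdrawal of Subjects. The phrase can equally mean ending the course of treatment rather than cutting a session short. At most it touches the final session of such a patient, if a reading was taken.

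**Conclusion.** No change to the protocol follows. It is silent on which last-session TDQ reading is the end-of-study value and on which session counts for a patient with fewer than 16. The two candidates differ by exactly the last session's acute effect, but the existence and size of that effect cannot be known from the document. This is an analysis-value definition of the kind a statistical analysis plan commonly supplies, and one may exist unseen.

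Three things keep the consequence small. All the data needed for either version are scheduled. The acute effect is assessed in its own right within the same endpoint, so it does not disappear under either choice. And imposing the pre-session reading would be a trade-off rather than a correction, because jaw opening at the end of treatment, last session included, is also a legitimate target for a symptomatic intervention.

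An analyst can fill the gap by showing the change to the last pre-session reading and the change to the last post-session reading, each labelled, beside the within-session change. With six patients and no hypothesis test stated in the protocol, that is enough. The conclusion assumes that the reading before session 1 serves as baseline and that both readings are in fact taken at each session, as scheduled.

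### Does counting stacked tongue depressors fail to measure the primary endpoint, which is a distance?

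*Protocol*

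**What the plan says.** The Protocol synopsis (Study Design) describes the jaw outcome as "The distance the mouth can be opened voluntarily". Study Primary Endpoints asks for change in inter-incisor or inter-gum distance, "both before and after each treatment session, and from baseline to the end of the study".

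Procedures Involved lists two severity measures, the tongue depressor quantity (TDQ) and the OMDQ-25. Only the TDQ concerns jaw opening: "Determine how many stacked tongue depressors the patient is able to fit safely between their front incisors". For edentulous patients who cannot wear dentures, "we will measure the distance between the front gums using the same method". The reason for the choice follows: "TDQ is a simple rapid measurement that is carried out routinely in speech therapy practice for evaluation and conservative treatment of jaw opening problems".

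The design section reads "Open-label pilot study". There are 6 patients with 16 sessions each ("or fewer sessions if individual patients experience discomfort or other problems", Study Timelines). The third objective is "Determine effect size, variability and distribution of data to allow rational design of a larger study".

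The Protocol states no depressor thickness, no conversion to millimetres, no rule for part-depressors, and no expected effect or SD.

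**The concern.** A distance is continuous, while a stack of depressors is a count. Read together, the endpoint and the procedure suggest that the trial records something other than what it names. Without a thickness, the count cannot be turned into a length. Three consequences would follow if that were right.

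- The third objective would suffer, because an effect size and SD in depressors might not carry over to a larger study.
- Rounding to whole depressors would inflate the SD of change, and with it the size of the next trial.
- The Protocol says that stacking is also used as conservative treatment. Two readings at each of 16 sessions make at most 16 × 2 = 32 stackings per patient, so the measurement might itself improve jaw opening.

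A ruler reading at the same visits looks like a nearly free remedy.

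**Working it through.** **1. Is the recorded unit different from the endpoint's unit?** The objectives, the endpoint and the synopsis name a distance and no unit, and no millimetre scale appears anywhere in the document. The sentence on edentulous patients says that the gum distance is measured by the TDQ method. The Protocol therefore defines an endpoint and an operational measure of it, and the two agree. What is absent is a scale factor. Multiplying every count by one constant thickness puts the data in millimetres, and the ratio of mean change to SD does not depend on that constant.

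**2. How much precision could a count cost?** The Protocol has no figure to reproduce. Depressor thickness t and the true SD of change s are assumptions, and the TDQ is taken as whole depressors. A reading in steps of t has rounding variance t²/12, and a change between two readings has t²/6. Against a 1 mm ruler:

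variance ratio = (s² + t²/6) / (s² + 1/6)

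| s (mm) | t = 1.0 mm | t = 1.5 mm | t = 2.0 mm | t = 3.0 mm |
|---|---|---|---|---|
| 1 | 1.00 | 1.375/1.167 = 1.18 | 1.667/1.167 = 1.43 | 2.14 |
| 2 | 1.00 | 4.375/4.167 = 1.05 | 4.667/4.167 = 1.12 | 1.32 |
| 3 | 1.00 | 9.375/9.167 = 1.02 | 9.667/9.167 = 1.05 | 1.15 |
| 5 | 1.00 | 25.375/25.167 = 1.01 | 25.667/25.167 = 1.02 | 1.05 |

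A simulation with counts rounded down (400,000 draws per setting, assumed baseline mean 20 mm and SD 6 mm, true mean change 3.00 mm) gave mean changes of 2.97 to 3.01 mm. At s = 3 and t = 2 the simulated SD was 3.108, against 3.109 by formula. The cost is in precision, not bias.

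**3. What would that mean for a later trial?** For two arms, an assumed 2 mm difference, 80% power and two-sided 5%, n per arm = 2 × variance × (1.960 + 0.842)² / 2². For the ruler, t = 1.5 and t = 2.0, rounded up:

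- s = 1: 5, 6, 7
- s = 2: 17, 18, 19
- s = 3: 36, 37, 38

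The difference is 1 to 2 patients per arm.

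**4. How does this compare with the noise of 6 patients?** With 5 degrees of freedom, the 95% interval of a variance runs from 5/12.83 = 0.39 to 5/0.831 = 6.0 times the estimate, and 6.0/0.39 is about 15. At s = 3 and t = 2, the 95% half-width for the mean change at n = 6 is 3.26 mm by count and 3.18 mm by ruler.

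**5. Does the ruler's advantage survive reading error?** The table sets reading error to zero for both tools. The excess rounding variance per reading is (t² − 1)/12, which is 0.104 at t = 1.5 and 0.25 at t = 2.0. The advantage is gone if the ruler's reading-error variance exceeds that of stacking by these amounts, equivalent to an SD of 0.32 or 0.50 mm. If both tools have a reading error of SD 1 mm, not already contained in s, then 2 × 1² = 2 is added to both variances. The ratios at s = 1 become 3.375/3.167 = 1.07 and 3.667/3.167 = 1.16. The Protocol gives no repeatability for either tool, so even the direction of the gain is not established.

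**The case for a change.** The best case for the concern is that the instrument is fixed at data collection. A SAP could convert counts if the thickness were known, but it could not recover lost resolution. The endpoint also includes change within each session. If those changes are small and vary little, the s = 1 row applies and rounding is no longer negligible. A ruler costs little and needs no extra visits.

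The point about resolution is true, but its size is unknown, because neither thickness nor SD is in the document. For within-session change, averaging 16 before-and-after pairs would bring the rounding SD down to √(0.375/16) = 0.15 mm to √(0.667/16) = 0.20 mm per patient at t = 1.5 to 2.0, if the errors are independent. This does not help the single baseline-to-end change. If the larger study also uses the TDQ, its planning needs the SD of the TDQ with its rounding included, which is what this pilot supplies.

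The repeated stacking is real as exposure, up to 32 times. The Protocol calls the reading rapid and describes no force or hold time, so an effect is conjecture. A ruler reading of maximum voluntary opening would still ask for the same effort up to 32 times. In an open-label study with no comparison group described, practice, expectation and time effects would remain under either tool. Swapping tools would also give up the within-session TDQ data that the Protocol chose to collect.

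**Conclusion.** The concern does not hold. The Protocol names a distance without a unit, states how it will be read, applies the same method to edentulous patients, and justifies the tool as simple, rapid and routine. Nothing in it is contradicted or stated wrongly. The thickness of a depressor and the scoring of part-depressors are details that a SAP, case report form or manual may hold.

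At assumed thicknesses of 1.5 to 2.0 mm, the count's variance of change is about 1% to 5% above a 1 mm ruler's when the true SD is 3 to 5 mm, and 18% to 43% above when it is 1 mm. At 1.0 mm there is no difference. These figures ignore reading error and take the count as whole depressors. The mean is not materially biased, and the 15-fold variance interval from 6 patients dominates throughout. Preferring a ruler is a reasonable taste on which statisticians may differ. The documents do not show it to be an improvement, and no change is needed.

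### Patients who must stop stimulation are removed from the study, and outcomes are scheduled only at baseline and at sessions, so early stoppers have no scheduled reading after their last attended session

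*Protocol*

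**What the plan says.** Under Study Primary Endpoints, jaw opening is to be compared "both before and after each treatment session, and from baseline to the end of the study", and quality of life is to be assessed by "measuring change in OMDQ-25 from baseline to the end of the study". The study summary gives each participant 8 weeks, and Procedures Involved plans 16 sessions in that time.

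Procedures Involved ties the measurements to sessions. For TDQ: "This will be measured before and after each treatment session". OMDQ-25 is taken at baseline and then following every session. The protocol describes no visit at early termination, no off-treatment follow-up and no week-8 visit separate from a session.

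Withdrawal of Subjects lists four grounds:
- Skin reaction: "Patients will be withdrawn from the study if they experience hyperemia at the electrode placement sites that does not resolve between patient sessions".
- Discomfort: withdrawal "if they experience more than mild discomfort that requires complete termination of neurostimulation at any point during the course of the study".
- Fatigue or weakness: "Patients will also be withdrawn from the study if they experience muscle fatigue or weakness which interferes with daily functions like speaking or chewing food".
- New implant: "Placement of a cardiac pacemaker, implanted defibrillator, or other implanted electronic device at any point during the study will also lead to withdrawal".

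Study Timelines also allows fewer than 16 sessions for discomfort or other problems, and attaches no assessment to the sessions missed.

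**The concern.** All four grounds are good reasons to switch off the current. None of them in itself prevents a patient from answering a questionnaire, and TDQ can be left out if it is unsafe. Because the rule ends study participation and the outcomes are tied to sessions, stopping treatment also stops measurement.

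The weakness ground matters most. Potential Benefits to Subjects says "Patients may experience functional improvement in activities impaired by jaw-closing dystonia, including speaking, chewing" and further activities. The withdrawal rule removes a patient whose weakness interferes with speaking or chewing. A patient harmed in the functions that the treatment is meant to help can therefore leave before that harm reaches OMDQ-25.

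At stake are the two baseline-to-end changes, and with them the effect size, variability and distribution that the secondary objective wants for planning a larger study. This is a matter of data collection. An analysis plan can choose how to treat a missing value, but it cannot supply a reading that was never taken.

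**Working it through.** The protocol states no stopping rate, effect size or precision target, so there is no figure of its own to reproduce. The check reads the schedule against the withdrawal rule and then illustrates the size.

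**Step 1: what remains after a stop.** Inputs: 16 sessions in 8 weeks (Procedures Involved). An even two sessions a week is assumed, since 16/8 = 2. After a stop following session k, the patient has k of 16 post-session OMDQ-25 readings and 2k of 32 TDQ readings, and 8 − k/2 weeks are unobserved.

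| Stop after session | OMDQ-25 kept | TDQ kept | Weeks unobserved |
|---|---|---|---|
| 4 | 4 of 16 | 8 of 32 | 6 |
| 12 | 12 of 16 | 24 of 32 | 2 |

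The baseline OMDQ-25 is kept as well.

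**Step 2: does the last reading capture the problem?** It depends on the ground.
- Hyperemia counts only if it persists between sessions, so it is recognised after the last completed session's readings.
- Weakness can appear between sessions. If the patient is then withdrawn before the next one, the last OMDQ-25 predates it. If it was already present at the last session, that reading may reflect it.
- Discomfort that ends stimulation arises in a session. The text does not say whether the post-session readings are still taken that day.
- A new implant is placed outside the sessions.

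**Step 3: two meanings of the study's end.** If it is each patient's last attended session, every patient treated at least once can have a value, but possibly one from before the problem and at a different time for each stopper. If it is week 8, the stopper has no scheduled value. The protocol does not say which applies.

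**Step 4: how often.** With an assumed stopping probability p per patient, independent between patients, P(at least one of 6) = 1 − (1 − p)^6.
- p = 0.05: 1 − 0.95^6 = 0.265
- p = 0.10: 1 − 0.90^6 = 0.469
- p = 0.20: 1 − 0.80^6 = 0.738

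If nobody stops, there is no effect.

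**Step 5: how much.** If m of 6 patients are left out and lie g SD from the others, on the same side, the mean of those remaining differs from the mean of all six by m × g / 6.
- m = 1: g = 0, 0.5, 1 gives 0, 0.083, 0.167 SD
- m = 2: g = 0, 0.5, 1 gives 0, 0.167, 0.333 SD

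The same formula applies if the last attended reading stands in, with g as the gap between that reading and the one not taken.

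For scale, the 95% confidence half-width for a mean change with all six patients is t(0.975, 5)/√6 = 1.049 SD. One stopper 1 SD away shifts the mean by 0.167/1.049, about one-sixth of that half-width.

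**The case against.** The strongest reply is that this is an open-label, single-arm pilot of six patients, with no randomised comparison for off-treatment follow-up to protect. The protocol never names a week-8 value and foresees shorter participation, so the last attended session is a fair reading of the study's end. A week-8 value after a stop at session 4 follows about six weeks without stimulation and may show washout or the underlying disease. The within-session TDQ comparison keeps every attended session. The protocol states no hypothesis test or decision threshold that could be overturned.

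Most of this stands, and it rules out several stronger readings that a reader might infer:
- *The primary changes are lost for every early stopper.* This holds only if the study's end means week 8, which the text does not fix. Nor does the protocol forbid a later reading; it simply schedules none.
- *The loss favours the device.* The documents do not support a direction. Hyperemia and a new implant have no stated link to outcome, and weakness of the masseters, which close the jaw, could even raise TDQ.
- *A week-8 visit would restore the precision of six patients.* With five values the half-width is t(0.975, 4)/√5 = 1.242 SD, against 1.049 with six. That gap is not a gain the visit can claim. An off-treatment reading is not exchangeable with completers' on-treatment readings, and pooling them would mix two treatment states in the SD wanted for planning.

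What the reply does not answer is that the last attended reading may come before the event that removed the patient, and nothing later is scheduled to show what happened.

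**Conclusion.** The point holds as a modest, cheaply remedied weakness of the design. The four grounds end study participation rather than stimulation alone, and no outcome is scheduled outside baseline and the sessions. An early stopper therefore enters the baseline-to-end changes through the last attended session, or not at all if the end is week 8.

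The loss may be informative, most plausibly for OMDQ-25 under the weakness ground, but its sign and frequency are unknown. The 26% to 74% chance of at least one stopper rests on assumed rates of 5% to 20% and independence between patients. The shift of 0 to 0.17 SD for one stopper, or 0 to 0.33 SD for two, rests on an assumed distance of 0 to 1 SD. Either is small beside the uncertainty already present with six patients. A patient who skips sessions but attends the last one is not affected by the gap at the end. The case for change is that the information cannot be recovered later and costs little to collect.

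**What to change.** In Withdrawal of Subjects, make the four grounds reasons to stop stimulation permanently, and reserve leaving the study for withdrawn consent or assent. The safety stop stays as it is.

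In Procedures Involved and Study Timelines, add wording such as: *Patients who stop stimulation early will be asked to complete OMDQ-25 and, if safe, TDQ when stimulation is stopped and again at week 8. If TDQ is omitted, the reason will be recorded.* The first of these readings can be taken at the visit where the stop is decided or in the next session slot already booked.

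Report both readings with the number of sessions received, and separately from the last on-treatment reading. Do not pool them with completers' values as if they were on treatment. The completers' schedule and the endpoint definitions need not change.

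The cost is wording in three short sections and at most one extra non-treatment visit, with a parking voucher, per early stopper. Some patients who found treatment uncomfortable may decline, and that should be accepted.
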